1.0 Introduction

1.1 Electrically Conductive Adhesive Solid Hydrogels

Electrically conductive adhesive solid hydrogels are used in the medical device field to provide an electrical interface to the skin of a subject to couple electrical signals into and/or out of the subject (e.g., for diagnostic and/or monitoring uses) and/or to couple electrical stimulus into the subject (e.g., for treatment and/or preventative uses).

Current hydrogels have been developed to be sufficiently adhesive to provide good skin adherence and good electrical contact thus ensuring an even spread of current density to prevent burns. At the same time, the hydrogels must be insufficiently cohesive to allow for easy removal from the skin¹.

A number of different hydrogel precursor formulations are commercially available. These generally include a monomer, a first initiator to promote polymerisation of the monomers in the precursor, a solubiliser, and a cross-linking agent. Some prior formulations have in the past exhibited undesirable properties including issues with adhesiveness, electrical conductivity, odour and skin irritation. It has been discovered that some of those problems are the result of poor polymerization of the monomers in the hydrogel precursors thereby leaving residual monomer and/or by-products, which can cause or result in some of the above undesirable properties.

The present hydrogels have unique and improved properties. More particularly, the present polymerising formulations or hydrogel precursors exhibit enhanced polymerisation, thereby reducing the amount of residual functional monomer and/or other monomeric residues in the hydrogel which are un-polymerised. The present hydrogels also desirably include a buffer system to help prevent discolouration and/or hydrolysis of the hydrogels as well as to improve shelf-life. Other additives can include conductivity enhancers, pharmaceuticals, humectants and skin health agents to provide for reduced skin irritation.

1.2 The geko™ T3 Neuromuscular Stimulation Device

The innovative geko™ T3 device manufactured by Firstkind Ltd (High Wycombe, United Kingdom), is a small, self-adhesive disposable, battery powered, neuromuscular stimulation device designed to enhance blood flow in the lower limbs.

The device is made from mylar (polyethylene terephthalate (PET)) and the electronic circuit is enclosed in a fully insulated polypropylene protective casing, so there is no risk of shock to the patient. The device also has charge-balanced waveforms that yield no build-up of charge in the patient, therefore, provided the device is used in accordance with the instructions for use, galvanic effects such as electrical burns cannot occur. The device is powered by battery and is thus totally isolated from the mains electricity supply. The primary lithium coin cell battery powering the device is removable for disposal. Please see Figure 1 for an illustration of the device (front view)

[figure not shown]

Figure 1: The T-3 geko™ device (front view).

The geko™ T3 device utilises an electronically conductive skin adhesive solid hydrogel (KM10T) that adheres to the skin and when applied externally to the leg on the lateral/posterior aspect of the knee, electrodes within the hydrogel layer stimulate the common peroneal nerve simultaneously activating the calf and foot muscle pumps that assist in returning blood to the heart. This simultaneous activation has the effect of increasing venous velocity and volume flow in the deep veins of the calf which in turn increases arterial and microcirculatory flow with no change to heart rate or blood pressure². Figure 2 shows an illustration of the device (rear view) with hydrogel layers and electrodes.

[figure not shown]

Figure 2: The T-3 geko™ device (rear view) with hydrogel layers and electrodes.

The geko™ T3 device has a range of stimulation levels to ensure activation of the muscle pumps irrespective of individual skin impedance balanced with patient comfort. The optimal stimulation level which maximises blood circulation varies between patients and is achieved when a stimulus results in a dorsi-flexion i.e. an involuntary upward outward movement of the foot. Please see Figure 3 for an illustration of the device fitted to the lower leg.

Figure 3: Administering non-invasive neuromuscular electrical stimulation via the geko™ T3 device applied at the peroneal nerve proximal to the posterior / anterior bifurcation.

The geko™ T3 device meets recognised International and European safety standards and is CE marked for its' indicated use in humans for increasing blood circulation and preventing venous thrombosis in patients known to be at high risk of venous thromboembolism (VTE). The device is currently in use within the NHS network as a mechanical VTE prophylaxis strategy for acute stroke patients.

1.3 Rationale

As outlined above, some hydrogel precursor formulations have previously exhibited undesirable properties including issues with adhesiveness, electrical conductivity and skin irritation. Some of these negative properties are the result of poor polymerisation of the monomer in the hydrogel precursors thereby leaving residual monomer and/or by-products, which can cause or result in the some of these undesirable effects. By adjusting the monomer component of the hydrogel precursor, polymerisation can be enhanced thus reducing the amount of residual monomer and/or by-products remaining and negating negative properties.

The KM10T hydrogel used in the geko™ T3 device is derived from an acrylic acid monomer and has good skin adhesion properties with low skin irritation. A new hydrogel designated KM40C has been developed that promises even lower skin irritation due to zero residual acrylic acid, following replacement of the acrylic acid monomer component of the hydrogel precursor with an acrylamide monomer. KM40C also promises good skin adhesion properties, like those of KM10T used in the geko™

T3 device.

As with KM10T, the new KM40C hydrogel formulation has been tested for safety in humans to current international biocompatibility standards (ISO10993) and subsequently, this new formulation has been used in the development of the geko™ device designated geko™ XT-3.

Both the T3 and XT-3 devices are identical in terms of the therapy they deliver to patients, they differ only in the hydrogel used for adhesion to the skin and although the new formulation promises good adhesion properties, this has not yet been tested in a clinical environment on patients receiving geko™ therapy.

As with the T3 device, the XT-3 device meets recognized, International and European safety standards and is also CE marked for its' indicated use in humans for increasing blood circulation and preventing venous thrombosis in patients known to be at high risk of VTE e.g. stroke patients

2.0 Objective

The aim of this study is to test the skin adhesion property of the new hydrogel KM40C during routine clinical use of the geko™ XT-3 device for VTE prophylaxis to ensure that skin adhesion is at least equivalent if not superior to the hydrogel KM10T incorporated into the geko™ T3 device which is currently in use in hospitals.

2.1 Study Endpoints

2.1.1 Primary Efficacy Endpoints

- Skin adhesion performance of new hydrogel formulation KM40C during routine clinical use of the geko™ XT-3 device will be compared to that of the current formulation used in the geko™ T3 device. Skin adhesion will be observed and scored numerically for statistical comparison to test for equivalency of the two formulations (new vs current).

2.1.2 Secondary Efficacy Endpoints

- The secondary endpoints are the incidence of adverse events (AEs), incidence of serious AEs (SAEs), incidence of study treatment related AEs, and the incidence of investigational device related AEs

3.0 Study Design

The study will be carried out at one clinical site and will be a non-blinded, non-randomised cohort observation study.

The study objective is to compare how well the geko™ device with a new skin adhesive (geko™ XT-3) sticks to the skin compared to that of the adhesive currently used to stick the current device (geko™ T3) to the skin. The performance of the new adhesive is expected to be at least the same if not better than the current one. This is an observational study or cohort study where the performance of the adhesives is observed and rated. There is no intervention to control the performance of the adhesives. As such, a randomized controlled trial is not required as the protocol does not aim to prove a causal relationship between an intervention and adhesive performance.

To enable a direct comparison of performance, patients will be divided naturally into two sequential groups or cohorts. This will also ensure that the XT-3 and T3 devices are not mixed during routine clinical use.

Group 1 patients will be consented and enter Phase 1 of the study. They will continue their treatment pathway with the geko™ T3 device as per hospital clinical protocol for VTE prevention. Group 1 patients will complete the 10-day, study period, before Group 2 patients are consented and enter Phase 2 of the study. Group 2 patients will continue their treatment pathway as per hospital clinical protocol but with the geko™ XT-3 device.

As both the T3 and XT-3 devices are identical in terms of the therapy they deliver to patients, the treatment pathway for both group 1 & 2 patients will be unaffected. The devices differ only in the hydrogel used for adhesion to the skin. Please see Figure. 4 for a schematic of the patient journey.

[figure not shown]

Figure 4: Schematic diagram of the patient journey for Groups 1 & 2.

3.1 Study Population

It is important that the skin adhesion strength of the new hydrogel formulation is evaluated together with that of the current formulation during clinical use of the geko™ devices. The use of healthy volunteers would not allow for this as the devices would not be being used in a population for the purpose for which they are intended. The study population will be patients who are immobile and bedbound following acute stroke, this population cannot be replicated within a healthy population.

Both hydrogel formulations have been tested for biocompatibility in humans and both geko™ devices are CE marked and indicated for use in humans for increasing blood circulation and preventing venous thrombosis in patients known to be at high risk of VTE. Please refer to Appendix 1 for a list of regulatory approvals.

As such, patients who have been admitted to the Acute Stroke Unit who will receive daily treatment with geko™ as an alternative VTE prophylaxis strategy as part of their standard care will be asked to participate.

3.2 Number of Participants

A total of 40 patients will be recruited, 20 into each phase of the study.

3.3 Eligibility Criteria

Eligible patients are those who meet all the following inclusion criteria and who do not have any listed exclusion criteria.

3.3.1 Inclusion Criteria

- Male or female aged ≥ 18 years
- Currently an in-patient hospitalised for acute stroke
- Use of geko™ as a mechanical prophylaxis strategy for venous thromboembolism
- Patient understands and is willing to participate in the study and can comply with study procedures

3.3.2 Exclusion Criteria

- Pregnancy or breast feeding
- Use of any neuro-modulation device other than geko™
- Participation in any other clinical study that may interfere with the outcome of either study

4.0 Schedule of Events

Procedures should take place in the following order:

4.1 Recruitment and Baseline (Day 0)

- Patient presents for geko™ therapy for VTE prevention following acute

stroke

- Confirm patient eligibility
- Obtain written informed consent
- Collect demographic data
- Fit geko™ device bilaterally for VTE prevention as per hospital standard care. The devices fitted will be as per allotted patient group and study phase.
- Record
 - Ease with which device fitted (rate from very easy to impossible)
 - Adhesion to patient's leg (rate from very well to not at all)
 - Use of additional fixation to keep the device in position
 - Ease of re-application if removed
 - Patient comfort (rate from very comfortable to extremely uncomfortable)
 - Device setting (1-11)
- Assess for any AEs

4.2 Follow-up and Daily Application of geko™ therapy (Days 1-9)

During daily review of the patient by a member of the healthcare team, a new geko™ device will be fitted bilaterally as per standard care. In addition, the following information will be collected each day or until the patient is able to mobilize independently:

- Length of time device worn for since fitting (hours)
- Adhesion to patient's leg (rate from very well to not at all)
- Use of additional fixation to keep the device in position
- Ease of re-application if removed
- Patient comfort (rate from very comfortable to extremely uncomfortable)
- Patient sleep post-fitting
- Patient's current mobility

Fit new geko™ device bilaterally for VTE prevention as per hospital standard care. Devices fitted will be as per allotted patient group and study phase and the following post-application information recorded:

- Ease with which device fitted (rate from very easy to impossible)

- Adhesion to patient's leg (rate from very well to not at all)
- Use of any additional fixation to keep the device in position.
- Patient comfort (rate from very comfortable to extremely uncomfortable)
- Device setting (1-11)
- Assess for any AEs

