6.6 Device Accountability

Patients will be receiving treatment with the device as part of their standard care for VTE prevention following acute stroke, therefore there is no requirement to provide product accountability instructions.

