8.0 Statistical Analysis and Sample Size Determination

8.1 Statistical Analysis

The ability of the geko™ XT-3 device to adhere to skin will be numerically scored and compared to the geko™ T3 using a non-paired t-test for equivalence.

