13.3 Archiving

All study documentation at the Study site and Sponsor site will be archived in accordance with Sponsor's quality standards and SOPs.

The Study site will maintain all research records, reports, and case history reports for a period of 15 years after study closure.

At the completion of the study, details of the archival process must be provided to the Sponsor. Study records are subject to inspection by applicable health and regulatory agencies at any time.

Records to be retained at the Study site include, but are not restricted to:

- Source data and the primary records upon which they are based (e.g., participant's progress notes, adverse event data, test results, and any other diagnostic procedures required to evaluate the progress of the study).
- Signed protocols and protocol amendments
- Product accountability records
- Study personnel signature log
- Monitoring logs
- Correspondence to and from the Sponsor, designee and IRB/IEC
- Principal Investigator and co-Investigator(s) Curriculum Vitae (CVs)
- Signed ICFs
- Patient screening and randomisation log
- SAE reports
- IRB / ICE approval letters and correspondence if applicable
- Other documents pertaining to the conduct of the study

These documents must be maintained and kept on file by the Study site so that the conduct of the study can be fully documented and monitored.

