Very Comfortable 	Comfortable 	Uncomfortable 	Very Uncomfortable 	Extremely Uncomfortable 

If any discomfort has been indicated, please provide a comment below:

Did the patient sleep with the device on?		Yes 	No 
---	--	------------------------------	-----------------------------

DAY 1: Application of geko™ device

Current mobility - Is patient able to walk independently? (If YES is selected patient CANNOT continue in the study - please complete EXIT form)				Yes 	No 
Study Phase	geko™ Device Fitted		Lot Number	Expiry Date	
Phase 1		geko™ T3			
Phase 2		geko™ X-T3			

CASE REPORT FORM	FOLLOW-UP 1 (DAY 1)			DATE (DD/MM/YYYY)	/	/
STUDY SITE: THE ROYAL STOKE UNIVERSITY HOSPITAL	PRINCIPAL INVESTIGATOR: [name]					

SITE NUMBER

0	2	5
---	---	---

 PATIENT NUMBER

0		
---	--	--

 PATIENT INITIALS

--	--

How easy was it to apply the geko™ device to the patients leg?

Very Easy 	Easy 	Difficult 	Very Difficult 	Impossible 
---------------------------------------	----------------------------------	---------------------------------------	--	--

If there were any difficulties, please provide a comment below:

Once applied, how comfortable for the patient was the geko™ device?

Very Comfortable 	Comfortable 	Uncomfortable 	Very Uncomfortable 	Extremely Uncomfortable 
--	---	---	--	---

If any discomfort has been indicated, please provide a comment below:

Which setting was the geko™ device set to?

1 	2 	3 	4 	5 	6 	7 	8 	9 	10 	11 

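### The Day 1–9 case report form lacks the post-fitting adhesion rating that Section 4.2 requires, and its one daily score names no device or leg, so some failures may go unscored

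*Combined protocol and SAP*

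**What the plan says.** Section 4.2 sets two blocks of data for each of Days 1–9. The first looks back at the device being taken off: "the following information will be collected each day or until the patient is able to mobilize independently". It covers hours worn, adhesion, fixation, re-application, comfort, sleep and mobility. The second concerns the new device: "Devices fitted will be as per allotted patient group and study phase and the following post-application information recorded". Its list again includes additional fixation and "Adhesion to patient's leg (rate from very well to not at all").

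Appendix 3 gives one form for Days 1–9. Its look-back block has one adhesion item, whose two worst categories are complete detachment and not sticking at all. Its application page opens with "How easy was it to apply the geko™ device to the patients leg", followed by comfort, setting and adverse events. It has no adhesion or fixation item. The Day 0 form has both after fitting.

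Fitting is bilateral, but each Day 1–9 form has one adhesion tick, one hours field and one row for device and lot. The re-application item covers a device that was removed and put back. Nothing covers a new device fitted between reviews.

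On analysis, Section 8.1 says adhesion will be "numerically scored and compared to the geko™ T3 using a non-paired t-test for equivalence". Section 8.2 bases the sample size on 80 devices with no failures. Section 6.6 says of devices used in standard care, "therefore there is no requirement to provide product accountability instructions", while Section 13.3 lists "Product accountability records" among the documents to be kept.

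**The concern.** Adhesion is the primary endpoint. Staff cannot follow Section 4.2 with the form supplied: on nine of the ten fitting days, the rating due straight after fitting has nowhere to go.

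The entries at risk are not a random subset. A device that will not stick, or that falls off and is replaced, is a failure of the property under study. If the next day's score is given to its replacement, the failure disappears from the outcome. That would move both gels towards good adhesion and make the zero-failure criterion in Section 8.2 easier to meet. The study is unblinded and the cohorts are sequential, so staff choose which device to rate while knowing the gel, and that choice could differ between phases.

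**Working it through.** **Inputs from the documents**
- Fittings on Days 0–9 and a final look-back on Day 10 (Sections 4.1–4.3).
- 20 patients per phase (Section 3.2).
- 80 devices, zero failures, four days of use, both legs (Section 8.2).

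**Assumed, because the documents are silent:** the true failure rate p, the share u of failures that go unscored, independence between devices, and the numerical coding of the adhesion scale.

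**Step 1. The plan's own figure.** 20 patients × 4 days × 2 legs = 160 devices, not 80. The figure 80 matches 20 × 4 × 1, one device per patient-day. Table 2 does give 80 at an AQL of 0.15 for lots of 51 to 1,200. The count needs reconciling, but the data-capture point does not depend on it. On the forms, one look-back tick per patient-day gives 20 × 4 = 80 scores for those 160 devices.

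**Step 2. Adhesion entries per patient**

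| | Section 4 text | Appendix 3 forms |
|---|---|---|
| Day 0 | 1 | 1 |
| Days 1–9 | 9 × 2 = 18 | 9 × 1 = 9 |
| Day 10 | 1 | 1 |
| Total | 20 | 11 |

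The shortfall is 20 − 11 = 9 per patient, or 9 × 20 = 180 per cohort if all stay 10 days. With the four days of use assumed in Section 8.2 (fittings on Days 0–3, last look-back on Day 4), the text gives 1 + 3 × 2 + 1 = 8 and the forms 1 + 3 + 1 = 5. The shortfall is then 3 per patient, or 60 per cohort.

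**Step 3. Following a failure through the forms**
- *Will not stick at the Day 3 fitting.* The text asks for an adhesion score that day. The form takes only ease of fitting, which runs to the impossible category and has a comment box. The Day 4 look-back can record failure to stick, or it can describe the device that was eventually worn.
- *Falls off and a new device is fitted before review.* Complete detachment can be ticked at review. No instruction says whether the tick, the hours and the lot belong to the lost device or its successor.
- *One leg detaches and the other holds.* There is one tick and no rule for choosing between legs or taking the worse.

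**Step 4. Zero-failure criterion, illustration.** P(no recorded failure in 80) = (1 − p(1 − u))^80.

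| p | u = 0 | u = 50% | u = 75% |
|---|---|---|---|
| 2% | 0.98^80 = 19.9% | 0.99^80 = 44.8% | 0.995^80 = 67.0% |
| 5% | 0.95^80 = 1.65% | 0.975^80 = 13.2% | 0.9875^80 = 36.6% |

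**Step 5. Mean scores, illustration.** Suppose a coding of 1 (best) to 5, with means of 1.3 for devices that hold and 4.5 for failures.
- Failure rate 5%: the full mean is 0.95 × 1.3 + 0.05 × 4.5 = 1.46. With half of the failures unscored it is (1.235 + 0.1125)/0.975 = 1.382.
- Failure rate 10%: the full mean is 0.90 × 1.3 + 0.10 × 4.5 = 1.62. With half unscored it is (1.17 + 0.225)/0.95 = 1.468.

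If one gel failed at 5% and the other at 10%, the difference would shrink from 1.62 − 1.46 = 0.16 to 1.468 − 1.382 = 0.086. No equivalence margin is stated, so this cannot be turned into an error rate.

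**The case against.** A reader might infer that a device failing at a Day 1–9 fitting, or replaced before review, leaves no scored record. The documents do not support that. Every Day 1–10 form has an adhesion item that includes both failure categories and a comment line for any detachment. A failure at fitting can therefore be scored a day late, and ease of fitting can mark it at once, though not on the adhesion scale.

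Nor can one say that no other record would show an extra device. The medical record is the primary source (Section 13.1), and device deficiencies go to the sponsor's complaints system (Section 9.2). Neither is tied to the endpoint, but either might mention a replacement.

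The replacement route is also not described in the plan. The documents provide for re-application and daily renewal. They do not say that devices are replaced between reviews, or that the rater would score the replacement. What stands is an ambiguity, not a known practice. Section 7.4 lists adhesion only once and the forms are headed as samples, so the second rating in Section 4.2 might be unintended. If so, the text needs correcting instead of the form, but the two still conflict.

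Finally, the zero-failure figures concern the sample-size rationale. Section 8.1 names an equivalence t-test as the comparison, and Section 8.2 does not say which adhesion category is a failure.

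**Conclusion.** The narrower point holds. The Day 1–9 form omits two items that Section 4.2 requires, which removes 9 of 20 adhesion entries per patient over the full period. The score that remains does not identify device or leg, and replacements have no item of their own. The counts follow directly from the documents.

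The effect on the result is possible but cannot be measured from the documents. The direction is clear: lost failures favour good adhesion for both gels, tend to shrink a real difference, and ease the zero-failure criterion. The move from 1.65% to 13.2% is an illustration. It assumes a 5% failure rate, half of failures unscored, and independent devices, although devices in fact cluster within 20 patients. Assuming that every early failure is lost would go beyond what the forms show.

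The contradiction between Sections 6.6 and 13.3 is secondary. Section 13.3 also lists a randomisation log in a non-randomised study, so the entry may be template text. It does mean that no device count can be relied on as a backup.

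**What to change.** 1. Add the adhesion and additional-fixation rows from the Day 0 form to the application page of the Day 1–9 form, as Section 4.2 already requires.
2. Record adhesion separately for each leg. Add to the Day 1–10 forms a line for the number of devices used since the last review, with the reason for each replacement (detached, would not stick, other).
3. State in Sections 2.1.1 and 8.4.1 that a device replaced because it detached or would not stick is scored in that category and counted in the Section 8.2 tally. Say in Section 8 which category is a failure and how several scores per patient are combined.
4. As secondary points, reconcile Section 6.6 with Section 13.3 on accountability records, and the 80 devices in Section 8.2 with the 160 that its own assumptions give.

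The cost is a form revision, a few sentences of protocol text and seconds per daily review. Recorded adhesion may look less favourable. The change concerns recording only and does not alter how devices are fitted or replaced.
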